Our objectives are to evaluate the effectiveness of “nudges” to clinicians, to patients, or to both in increasing in TUTS referral and engagement; and to explore clinician, patient, inner setting (e.g., clinic), and outer setting (e.g., payment structures) mechanisms related to TUTS referral and engagement. We will employ rapid-cycle approaches to optimize the framing of nudges to clinicians and patients prior to initiating the trial and mixed methods to explore contextual factors and mechanisms.

We will conduct this study with at least 100 clinicians and at least 900 smokers across Penn Medicine’s ACC (the clinician sample size may increase with additional clinicians joining Penn and the patient sample size may be higher given the pragmatic design and delay between determination of eligibility [i.e., patient smokes] and nudge delivery at a subsequent visit). We

expect the study to yield essential insights into the effectiveness of nudges as an implementation strategy to speed the uptake of high value evidence-based TUT within cancer care, and to advance our understanding of the multilevel contextual factors that drive response to these strategies. These results will lay the foundation for how cancer care settings can ensure that patients with cancer who smoke are engaged with evidence-based TUT and may lead to a future R01 focused on scaling-up this approach across other cancer centers involved in the C3I.

OBJECTIVES

Aim 1: Conduct a four-arm pragmatic cluster RCT to test the effectiveness of nudges to clinicians, nudges to patients, or nudges to both in increasing TUTS referral and engagement in cancer patients who smoke, vs. usual care (UC). H1a: Each of the implementation strategy arms will significantly increase TUTS referral and engagement compared to UC. H1b: The combination of nudges to clinicians and to patients will be the most effective.

Aim 2: Conduct a quantitative evaluation using secondary data (obtained via EMR, for patients, and by survey, for clinicians) to identify moderators of implementation effects on TUTS referral and engagement. H2: Nudge impact will be moderated by clinician, patient, and inner setting factors. [Note: the clinician survey will be conducted within a separate study funded by this grant and submitted for IRB approval as a separate protocol; data across the studies will be linked by clinician name and study ID.)

Primary outcome variables:

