- 2) Prescribing authority in Pennsylvania (i.e., physician, nurse practitioner, physician assistant)
- 3) Cared for at least 1 tobacco-using patient in 30 days prior to recruitment
- 4) English-speaking (messages will be in English)

Patient participants must be diagnosed with cancer and report current tobacco smoking (as assessed by any staff collecting vital signs or initially rooming the patients such as nurses, front desk staff, MAs, nursing assistants or technicians during an Index Visit). Patients are considered in the analyzable dataset after their Index Visit and after they have a clinic visit with a clinician in the study at which point a nudge may have been delivered (see steps below).

The process by which patients become eligible for inclusion involves a 3-step algorithm employed in the EMR:

- Step 1 – All patients seeking care within the participating Abramson Cancer Center programs are screened for tobacco use status in order to ascertain relevance to the project (i.e., tobacco exposure). This screening encounter need not be a visit with a clinician who is in the cluster randomization.
- Step 2 – This step occurs at the first visit with a clinician within the cluster randomization. Note that this might be the same encounter in which screening occurs, but does not have to be. At this visit, all patients identified as current smokers are assigned a hidden (i.e., system) variable, the value of which is based on the clinician they are scheduled to meet during that visit (i.e., cluster membership).
- Step 3 – The logic is engaged at the next (third in series) visit, wherein the system variable is used to guide the intervention based on the clinician's cohort. There must be this visit to permit the delivery of the nudges (or not, if in usual care arm). The primary outcome is clinician referral for tobacco cessation through the EHR at this visit. Thus, patients eligible for this study are only those who are screened (and positive for tobacco use) and have completed the two visits in their randomly assigned cluster (clinician clusters are the unit of randomization) during the study period.

3. Subject Recruitment and Screening:

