6. Statistical Analysis:

Based on our preliminary data, we anticipate including at least 900 smoking patients (based on prevalence estimate of ~7% among 13,000 patients screened over a 1-year study period), nested within at least 100 clinicians. Analysis will use the first TUTS order generated for each patient/physician combination. Data are clustered within clinician, and the exchangeable correlation observed from other studies is small (0.07). We calculated power requirements by simulation using Stata 15, assuming a logistic regression model fitted using generalized estimating equations (GEE), and found our sample gives us 80% power to detect 11% improvement in our primary outcome (e.g., from current 34% referral rate to 45%), using a two-sided type 1 error rate of 5%, for planned comparisons between usual care and each individual nudge arm. The effect of the combined nudge arm is expected to be larger than each individually, indicating at least 80% power to detect probable effects for the comparison between usual care and the combined arm.

We have defined our intention to treat (ITT) sample using the coding algorithm that makes intervention possible, irrespective of whether a nudge was delivered or received. Thus, the ITT cohort is comprised of all eligible patients, defined as those who screened positive for tobacco exposure and have completed the two visits in their randomly assigned cluster. Eligible patients may or may not receive the nudge to which they were assigned and may or may not have access to MyPennMedicine; regardless, all eligible patients are analyzed in the ITT sample.

We have patient-level data on all those screened positive for tobacco but who did not complete the subsequent visits with a clinician in our cluster randomization (e.g., patient came for the first visit where the hidden system variable was assigned and never returned). While these patients are not considered eligible for our trial, they are part of the “screened” population, and we can compare them to our eligible patients on available data to assess the generalizability of our sample.

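### The rule for choosing the primary-analysis record (first order per patient/physician pair) is not tied to the visit, the assigned cluster or the ITT cohort that define the primary outcome

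*Combined protocol and SAP*

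**What the plan says.** Key Eligibility Criteria sets out three steps. Step 1 is tobacco screening, which need not involve a randomised clinician. Step 2 is the first visit with a randomised clinician, when the patient receives one hidden variable giving cluster membership. On whether Steps 1 and 2 can coincide, it says "Note that this might be the same encounter in which screening occurs, but does not have to be". Of Step 3 it says "The logic is engaged at the next (third in series) visit", and then "The primary outcome is clinician referral for tobacco cessation through the EHR at this visit".

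Statistical Analysis, in the paragraph on sample size, says "Analysis will use the first TUTS order generated for each patient/physician combination". Two sentences cover the population. One describes patients as nested within clinicians. The other, in the ITT paragraph, includes every patient who screened positive and completed two visits in the assigned cluster, whether or not a nudge reached them.

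Study Measures defines the primary measure as signed TUTS orders over pended TUTS orders. Study Intervention Phase says staff place a pended order once they identify a current smoker at check-in. The overview before the Objectives mentions a "delay between determination of eligibility [i.e., patient smokes] and nudge delivery at a subsequent visit".

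**The concern.** The primary outcome is fixed by a visit and by one cluster per patient. The record rule is fixed by order sequence and by patient/physician pair. Nothing says which governs, so two analysts could build different primary datasets from the same EMR extract, each able to cite the plan.

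Two consequences matter. If the first order was decided before the clinician nudge was active, the analysed outcome is one that the nudge could not have changed for that patient. If a patient has records under two randomised clinicians, the patient may contribute to two arms, although the algorithm assigns only one.

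**Working it through.** The plan attaches no figure to the record rule, so there is nothing to recompute. The check is a comparison of the definitions.

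| Place | Unit | Visit or order | Cluster | Who is counted |
|---|---|---|---|---|
| Key Eligibility Criteria, Steps 2 and 3 | Patient | Step 3 visit | One, set at Step 2 | Screened positive, two visits in the cluster |
| Statistical Analysis, record rule | Patient/physician pair | First order, no visit named | Not stated | Pairs with an order |
| Statistical Analysis, ITT paragraph | Patient | Not stated | The assigned one | All eligible patients |
| Study Measures | Order | Not stated | Not stated | Pended orders |

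Following patients through the algorithm shows where the rules can part.

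1. *Screening and Step 2 are the same encounter.* Staff pend an order at check-in, and the randomised clinician may sign or cancel it there. The nudge logic engages only at the next visit. The first order for the pair is then a pre-nudge decision, while the stated outcome is what happens at Step 3. That decision would probably precede the patient message too, since the message follows screening and refers to an upcoming appointment.
2. *Screening comes first, and an order is decided at Step 2.* Under Key Eligibility Criteria the logic still waits for Step 3, so the first order for the pair again precedes the clinician nudge.
3. *The patient sees a second randomised clinician.* Physicians, nurse practitioners and physician assistants are all eligible, so this is possible. A pair rule permits a second record, and the two clinicians may be in different arms.
4. *An eligible patient has no pended order.* The patient belongs to the ITT cohort but is absent from the Study Measures denominator and has no record under the pair rule.

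The rules agree if every ITT patient has one randomised clinician and the first order for that pair is the one decided at Step 3. No section states this.

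*Direction of bias in cases 1 and 2.* A decision taken before the nudge has the same expected referral rate in every arm, so mixing such decisions with nudged ones shrinks the difference. This assumes that a clinician's nudges for other patients do not carry over to the early decision.

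*A separate timing question.* Study Intervention Phase shows the clinician nudge at the next visit after screening. If screening and Step 2 coincide, that is Step 3 and the sections agree. If they are separate, it can be Step 2, which conflicts with Key Eligibility Criteria. Case 2 depends on how this is resolved.

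**The case against.** The best reply is that the sentence only removes duplicates within a dataset already defined elsewhere. It sits in the sample-size paragraph. Key Eligibility Criteria says "Patients are considered in the analyzable dataset after their Index Visit and after they have a clinic visit with a clinician in the study", and the ITT paragraph relies on the same algorithm and a single cluster. This is a plausible reading of the intent. But the sentence is worded as an analysis rule, and the model description that follows gives no other record rule. The ITT paragraph settles who is included, not which order supplies the outcome.

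A second reply is that early decisions may not occur in practice. The description of order pending concerns what Epic currently does for new patients, and the alert is said to be modifiable. At the nudge visit the clinician is presented with an order, which suggests that one is available then, at least in the clinician-nudge arms. This stands, and it is why no frequency can be assumed.

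A third reply is that a patient-based denominator changes the measure in Study Measures, and that scoring an already referred patient as 0 is unattractive. The first half is answered by the ITT paragraph, which already requires all eligible patients. The second half is a real cost and needs a sensitivity analysis.

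A reader might go further and infer a definite dilution of the planned rise from 34% to 45%, or a loss of power. The documents do not support this. They give no share of orders settled before Step 3, and do not say whether such orders are pended again or whether referred patients are referred a second time. Nor can the mismatch be confined to patients screened and assigned at one encounter: cases 2 to 4 are other routes.

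**Conclusion.** The point holds as an inconsistency in the definition of the primary dataset, and it should be fixed. Read literally, the record rule does not match the stated primary outcome or the ITT cohort, and the Study Measures denominator does not match the ITT cohort either. The possible bias in cases 1 and 2 is toward no effect, given no carry-over between a clinician's patients. Its size is unknown and may be zero, because the documents do not report how many orders are settled before Step 3, how many patients see two randomised clinicians, or how many eligible patients lack a pended order. The conclusion rests on the text alone; it does not claim that the trial's result is biased.

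**What to change.** Replace the record rule in Statistical Analysis with: *One record per ITT patient, analysed in the arm and clinician cluster assigned at Step 2; outcome = 1 if a TUTS referral order is signed at the Step 3 visit, 0 otherwise.* In addition:

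- State whether an order signed at that visit by a clinician other than the assigned one counts.
- Align the primary denominator in Study Measures with the ITT cohort, and keep signed over pended orders as a supportive measure.
- State, from the EMR build, whether an order settled before Step 3 is pended again at Step 3.
- Report by arm how many orders were signed or cancelled before Step 3.
- Add a sensitivity analysis that counts an earlier signed referral as 1.
- Separately, reconcile Key Eligibility Criteria and Study Intervention Phase on the visit at which the clinician nudge appears, and keep the record rule consistent with the result.

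The cost is protocol and SAP wording plus one extraction rule applied to routinely collected EMR data. There are two drawbacks. Patients referred before Step 3 count as 0 in the primary analysis, which the sensitivity analysis addresses. And if settled orders are not pended again, the new rule removes the ambiguity but not the dilution; the by-arm counts would show how far that matters.

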For Aim 1, we will analyze all binary outcomes using logistic regression with GEE. The study design is factorial, and models will contain binary predictor terms for clinician and/or patient prompt. We will conduct stratified analyses by MPM access. We will also include adjustments for time in months, fixed effects for site, and random effects for clinician. We will control for type 1 error inflation by hierarchical testing, starting with the overall model significance, followed by effect of clinician prompting, followed by patient prompting. Once we have fitted the main effects model, we will test for interaction between clinician and patient prompts, and retain that interaction term if significant (alpha=5%). For Aim 2, variability in these outcomes by treatment arm and moderators will be assessed using interaction terms within logistic regression models. We will fit an adjusted logistic regression model using the same approach described in the primary analysis. Covariates of interest available through the EMR and clinician survey will be added to the model, including patient-level (e.g., cancer type), clinician-level (e.g., years in practice), practice-level (e.g., community vs. hospital-based), and ecological data.

RISK/BENEFIT ASSESSMENT:**1. Risks:**

There are minimal risks to participants in this trial. Regardless of nudges, treatment provided is FDA approved, clinicians routinely order treatment as part of their standard of care, and patients routinely use these smoking cessation treatments. The interventions could increase the time spent discussing smoking cessation with patients. However, shared-decision making is a high priority and evidence-based practice for cancer care and increased time on this topic is likely valuable. In our prior studies, nudges in the EMR were associated with minimal burden on practice staff and clinicians. There is a risk of breach of data and confidentiality, however we described the precautions in place to securely manage this data in the "Data Management" section of this protocol.

2. Benefits:

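### The stated 80% power for each single-nudge arm against usual care is about 48% at the stated sample; only the factorial main effects come near 80%, and only without interaction

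*Combined protocol and SAP*

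**What the plan says.** The power statement is in the first paragraph of Statistical Analysis (Study Procedures, item 6). It takes at least 900 smoking patients nested in at least 100 clinicians and says that "the exchangeable correlation observed from other studies is small (0.07"). On method it says "We calculated power requirements by simulation using Stata 15, assuming a logistic regression model fitted using generalized estimating equations (GEE"). The result is that the investigators "found our sample gives us 80% power to detect 11% improvement in our primary outcome (e.g., from current 34% referral rate to 45"%, two-sided at 5%, "for planned comparisons between usual care and each individual nudge arm". For the combined arm it expects a larger effect than for either nudge alone, "indicating at least 80% power to detect probable effects for the comparison between usual care and the combined arm". It gives no combined-arm referral rate and no simulation settings (allocation, cluster sizes, model terms).

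H1a (Objectives, Aim 1) is also worded arm by arm: each strategy arm is to beat usual care. The Detailed Description randomizes clinicians to four arms.

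The Aim 1 analysis paragraph of the same Statistical Analysis section is built differently: "The study design is factorial, and models will contain binary predictor terms for clinician and/or patient prompt". Testing is hierarchical, "starting with the overall model significance, followed by effect of clinician prompting, followed by patient prompting". Then: "Once we have fitted the main effects model, we will test for interaction between clinician and patient prompts", with the interaction term kept if significant at 5%. No stand-alone comparison of an arm with usual care is listed.

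**The concern.** Four arms share 900 patients, so a comparison of one nudge arm with usual care uses about half of them, and clustering by clinician reduces that further. An 11-point difference with about 225 patients per arm is short of 80% power even before clustering.

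A reader will take the 80% as the power of the comparison that the text and H1a both name. If the true figure is near 50%, a non-significant single-nudge result would be read as stronger evidence against that nudge than it is. The planned model tests different quantities, factorial main effects, so the powered comparison, the hypothesis and the analysis do not visibly line up.

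**Working it through.** **Inputs.** From Statistical Analysis: 900 patients, 100 clinicians, correlation 0.07, 34% against 45%, two-sided 5%. From the Detailed Description: four arms. Assumed, because not stated: equal allocation, equal cluster sizes unless noted, no covariate adjustment.

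**Arm against usual care**

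- Patients per arm: 900/4 = 225. Clinicians per arm: 100/4 = 25. Cluster size: 225/25 = 9.
- Design effect: 1 + (9 − 1) × 0.07 = 1.56. Effective n per arm: 225/1.56 = 144.2.
- Variances: 0.34 × 0.66 = 0.2244 and 0.45 × 0.55 = 0.2475; sum 0.4719.
- SE = √(0.4719/144.2) = 0.0572; z = 0.11/0.0572 = 1.92; power = Φ(1.92 − 1.96) = **48.5%** (48.0% with a pooled variance).
- No clustering: SE = √(0.4719/225) = 0.0458; z = 2.40; power = **67.1%**.

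The stated 80% is therefore not reproduced.

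**Simulation.** Logistic GEE with robust variance and beta-binomial clusters at correlation 0.07 gave 47% to 51% for this contrast with equal clusters. With unequal clusters (coefficient of variation 0.54 and 0.77) it gave 45% to 48%. Null rejection was 5.2% to 6.7%, so these powers are if anything slightly optimistic.

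**Other settings tried for the same contrast**

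| Setting | Power |
|---|---|
| One-sided 5%, clustered | 61% |
| One-sided 5%, no clustering | 77% |
| 900 patients spread over 275 clinicians | 60–61% |
| 2,300 patients, 275 clinicians (full pool in Target Population and Accrual) | 87–88% |

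No setting with 900 patients in four equal arms reaches 80%.

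**What 80% would take**

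- n per arm = (1.960 + 0.842)² × 0.4719/0.11² × 1.56 ≈ 478. That is about 1,910 patients in all, or 212 clinicians at 9 each. Without clustering it is about 1,224 patients.
- At 900 patients and 100 clinicians, the difference detectable with 80% power is about 16 points (34% to 50%).

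**Main-effects model**

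- ln OR = ln(0.45/0.55) − ln(0.34/0.66) = 0.463 (OR 1.59). If effects add on the log-odds scale, the combined-arm rate is 56.5%.
- Information per arm, effective n × p(1 − p): usual care 32.4, each single-nudge arm 35.7, combined 35.4.
- Information on the clinician-prompt term: 1/(1/32.4 + 1/35.7) + 1/(1/35.7 + 1/35.4) ≈ 17.0 + 17.8 = 34.8. SE = 1/√34.8 = 0.170.
- Power = Φ(0.463/0.170 − 1.96) ≈ **77.9%**; 76.9% if only the clinician nudge works. Simulated: 77% to 79% with equal clusters, 74% to 77% with unequal clusters.
- About 950 patients in 106 clinicians gives 80%.
- If all three nudge arms sit at 45%, so that the combination adds nothing, simulated main-effect power falls to about 27%.

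**Combined arm against usual care** (effective n 144.2 per arm)

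| Combined-arm rate | Power |
|---|---|
| 45% | 48.5% |
| 47% | 62% |
| 49% | 74% |
| 50% | 80% |
| 56.5% (additive log-odds) | about 97% |

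**The case against.** The strongest reply is that the design is declared factorial. In the planned main-effects model, each prompt coefficient is the model's estimate of that nudge against usual care. On that reading the stated inputs give about 78%, and small changes close the gap: about 950 patients, or about 115 clinicians, or a correlation near 0.06. The sample is also a floor, and the analysis takes the first order per patient and physician pair, so analysed units may exceed patients.

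This is a plausible source of the 80%, but only an inference, since no settings are reported. It also depends on no interaction, which the power statement does not say. The plan itself tests for interaction and keeps the term if significant. With 0/1 coding, the prompt coefficients then become the single-nudge arms against usual care, back at about 48%. So the planned model can supply the contrasts H1a needs, but the plan does not say which term tests H1a.

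The larger pool would give adequate arm-wise power, but the power claim rests on 900 and 100.

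On the combined arm, the plan's logic is sound if 80% for a single arm is granted, and under additive log-odds the conclusion holds comfortably. Because the single-arm figure fails, an effect merely larger than 11 points no longer guarantees 80%; a rate of about 50% is needed.

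**Conclusion.** The concern holds. For the comparison the power statement names, power at the stated minimum sample is about 48%, not 80%, and about 67% with no clustering at all. The closed form and simulation of the named GEE approach agree. The figures rest on equal four-way allocation, equal clusters and no covariates; unequal clusters lower them slightly.

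The consequence depends on how H1a is to be tested. By main effects with no interaction, the shortfall is minor (about 78% against 80%). By stand-alone arm contrasts, or by the model with the interaction retained, a true 11-point gain is missed about half the time. The plan does not settle which applies. The combined-arm claim is supportable only once an assumed rate of roughly 50% or more is stated.

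**What to change.** Rerun the power simulation, report its settings (allocation, cluster-size distribution, model terms), and reword the power paragraph so that:

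- the figure near 80% is attached to the factorial main effects, with the no-interaction assumption stated (about 78% in this check);
- the power of each single-nudge arm against usual care at 900 patients and 100 clinicians is given for 34% against 45% (about 48% here), with the difference detectable at 80% power (about 16 points);
- the combined-arm rate behind its power claim is stated;
- H1a says whether it is tested by the main-effect terms or by stand-alone arm contrasts and, if the latter, the Aim 1 analysis paragraph lists those contrasts.

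The numbers above are check values, to be replaced by the sponsor's rerun. The cost is one simulation and some wording, with no added enrolment. The price is a less favourable stated power for the arm-wise comparisons, which will be seen to be underpowered at the minimum sample.

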Aim 2 measures, collected through the EMR, will include patient age, sex, race/ethnicity, type of health insurance (e.g., Medicare, Medicaid, Commercial), address, cancer type, and history of prior tobacco cessation pharmacotherapy. Clinician-level data will be collected by survey led by a separate study funded by this grant and approved by the IRB: site, years in practice, patient panel size, the prevalence of patient smoking in the patient panel, and type of oncologist (medical, radiation, surgical). Additional data will include practice-level data: setting (community vs. hospital-based), urban vs. non-urban location, and health insurance mix.

2. Administration of Surveys and/or Process:

Aim 1. No surveys will be administered as part of this study.

Aim 2. Any surveys used as part of this aim will be submitted to the IRB under a separate study protocol prior to use.

3. Data Management:

To minimize the risk of breach of data and confidentiality, we will use secure, encrypted servers to host the data and conduct the analysis. The Digital Academic Research Transformation (DART) will be the hub for the hardware and database infrastructure that will support the project. DART provides a secure computing environment for a large volume of highly sensitive data, including clinical, genetic, socioeconomic, and financial information. DART requires all users of

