We seek to improve TUTS referral and engagement by overlaying normative framed messages to address clinician and patient biases. Upon opening the Epic Order tab at a patient’s next visit after the screening encounter, clinicians will receive the implementation strategy, placed directly over the order interface. The clinician will be required to “acknowledge” or “opt-out” when presented with the order. Opting-out will require clinicians to acknowledge a reason for opt-out using a checklist or free text.

Nudges to Patients. Patients will receive a message sent through myPennMedicine following establishment of their smoking status (at the screening encounter). In all cases, the message will include information specific to the upcoming appointment with the oncology clinician.

Nudges to both clinicians and patients. Both strategies described above will be used.

Usual care. Clinicians and patients will receive no further interventions beyond usual practice. In early 2019, all Penn Medicine ACC clinicians receive the opportunity to refer to TUTS without nudges.

Message design and testing. Messages will be framed to undermine biases. We will optimize the framing of the messages using rapid-cycle approaches to ensure face validity and maximum effect

3. Data Collection:

The EMR and other Penn Medicine secondary databases (the TUTS program) will be used to collect information on practices, clinicians, and patients. These systems are used to routinely collect this information for patient care. We will also collect data from the census via publicly available datasets. Once collected, data are maintained on password-protected computers. [name], who directs the PENN DMS, will oversee the DMS for this study. ORACLE and MS ACCESS permit real-time data entry, storage, and QA by web-based remote access and scannable forms which increases standardization across personnel. We have >15 years of experience with this DMS for smoking cessation trials. The DMS generates database tables, constructs semantic constraints on fields, and is used for data entry, storage, retrieval, and security. The DMS uses visit dates to describe procedures and measures to be ascertained. The DMS mimics the appearance of CRFs which are completed at each visit. Each visit date is “milestoned” (e.g., completed, scheduled, missed). Clinician data will be ascertained by a survey conducted under a separate IRB protocol and funded by this grant.

4. Genetic Testing:

n/a

5. Use of Deception:

n/a

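### The stratified analyses by MPM access include no prompt-by-access interaction, so they cannot show whether a nudge's effect depends on portal access

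*Combined protocol and SAP*

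**What the plan says.** The Aim 1 text in Study Procedures, 6. Statistical Analysis, contains the single sentence "We will conduct stratified analyses by MPM access". It gives no role, test, alpha, outcome list or time at which access is determined. MPM is read here as myPennMedicine.

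The same paragraph controls type 1 error by "hierarchical testing, starting with the overall model significance, followed by effect of clinician prompting, followed by patient prompting". No access stratum is a step in that sequence. The one interaction named for Aim 1 concerns the two prompts: "we will test for interaction between clinician and patient prompts, and retain that interaction term if significant (alpha=5" percent).

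For Aim 2, "variability in these outcomes by treatment arm and moderators will be assessed using interaction terms within logistic regression models". MPM access is not among the example covariates there. Nor is it in the patient-level EMR measures listed under Methods, 1. Study Measures: "patient age, sex, race/ethnicity, type of health insurance (e.g., Medicare, Medicaid, Commercial), address, cancer type, and history of prior tobacco cessation pharmacotherapy".

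Two other statements matter. Study Intervention Phase describes the patient nudge as a portal message: "Patients will receive a message sent through myPennMedicine following establishment of their smoking status (at the screening encounter"). The ITT definition keeps everyone: "Eligible patients may or may not receive the nudge to which they were assigned and may or may not have access to MyPennMedicine".

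**The concern.** Only patients with portal access can receive the patient nudge, while the ITT set includes patients without it, who dilute the all-patient effect. Whether the effect depends on access is therefore a question that readers will ask, and looking at it is sensible. The planned method does not answer it. Two separate fits give two estimates and two p-values, and a significant result in one stratum beside a non-significant one in the other is not evidence of a difference. The problem also touches the clinician prompt, which does not use the portal: splitting the sample will often make an equal effect look unequal.

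There is a second, conditional issue. If the all-patient test of the patient prompt fails or is never reached in the hierarchy, the access stratum is the natural place to look for a positive result, and the plan does not say how such a result may be used.

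**Working it through.** **Inputs.** From Statistical Analysis: at least 900 patients, at least 100 clinicians, exchangeable correlation 0.07, 34% versus 45% referral, two-sided 5%, 80% power. Assumed: four equal arms, 900/100 = 9 patients per clinician, and an access share *a* of 50% to 90%, because the documents give none.

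**1. The plan's power figure.** The design effect is 1 + (9 − 1) × 0.07 = 1.56.
- Single arms: 225/1.56 = 144.2 effective patients per arm, power 48% (49% by simulation).
- Factorial margins: 450/1.56 = 288.5 per side, power 77% (77.5% by simulation).

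The stated 80% is not reproduced for the arm comparisons that the plan names. That is a separate matter. The main-effect test is close to 80%, so step 2 takes 80% as given and then repeats the check from the plan's inputs.

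**2. Same true effect in both strata.** 80% power corresponds to a noncentrality of 1.96 + 0.84 = 2.80. The strata have δ₁ = √a × 2.80 and δ₂ = √(1 − a) × 2.80. Each has power p = Φ(δ − 1.96) + Φ(−1.96 − δ). With independent strata, P(exactly one significant) = p₁(1 − p₂) + p₂(1 − p₁).

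| Access share | p₁ (access) | p₂ (no access) | Exactly one significant |
|---|---|---|---|
| 50% | 0.508 | 0.508 | 0.50 |
| 60% | 0.583 | 0.425 | 0.51 |
| 70% | 0.650 | 0.335 | 0.55 |
| 80% | 0.707 | 0.240 | 0.61 |
| 90% | 0.757 | 0.144 | 0.68 |

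Using factorial margins and within-stratum design effects instead gives 49%, 58% and 66% at shares of 50%, 80% and 90%.

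**3. Shared clinicians.** One clinician can have patients in both strata, so the stratum statistics are correlated. With m patients per clinician in a stratum, the variance of the clinician's stratum mean is proportional to v = [1 + (m − 1) × 0.07]/m, and the correlation is 0.07/√(v₁v₂).
- *a* = 50%: m = 4.5 in each stratum, v = 1.245/4.5 = 0.277, correlation 0.07/0.277 = 0.25.
- *a* = 90%: v₁ = 1.497/8.1 = 0.185, v₂ = 1/0.9 = 1.111, correlation 0.07/√0.206 = 0.15.

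At a common correlation of 0.2, with overall power held at 80%, the bivariate normal calculation gives about 0.43 at a 50% share. At 90% the correlation changes little, and the result stays at about 0.68. Using 0.25 at the 50% share lowers that end to about 0.40.

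**4. Global null.** A patient-prompt claim through the hierarchy needs the clinician and patient tests both significant: 0.05 × 0.05 = 0.0025, or 0.25%. The overall-model gate is then passed automatically, since 2 × 1.96² = 7.68 exceeds the 2-df critical value of 5.99. If a 5% test in the access stratum also counted as a claim, the chance lies between 0.05 and 0.05 + 0.0025 = 0.0525; simulation gives about 5.1%.

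**5. Power of an interaction test.** Take +11 points with access and 0 without, factorial margins, strata treated as independent.
- *a* = 50%: effective n = 225/1.245 = 180.7 per side in each stratum. The variance is (0.34 × 0.66 + 0.45 × 0.55)/180.7 + 2 × 0.34 × 0.66/180.7 = 0.00261 + 0.00248 = 0.00509. SE = 0.0714, z = 0.11/0.0714 = 1.54, power 34%.
- *a* = 90%: effective n = 405/1.497 = 270.5 and 45 (design effect set to 1). The variance is 0.4719/270.5 + 0.4488/45 = 0.00174 + 0.00997 = 0.01172. SE = 0.108, z = 1.02, power 17%.

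**The case against.** The strongest reply is that the plan does nothing wrong here. It assigns the strata no alpha and no claim rule. The confirmatory tests use all eligible patients regardless of access, and an analysis outside a stated hierarchy is ordinarily read as supportive. Looking by access has a clear rationale when the nudge travels only by portal. All of this stands, and it is why the point concerns the method for comparing strata and not the primary inference.

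A reader might go further and infer that Aim 1 carries a total error of about 12% (hierarchy plus two patient-prompt stratum tests) or 19% (plus all four stratum tests). The documents do not support that. Those totals require every stratum test to be a confirmatory claim, which the plan never says. They count significance among patients who cannot receive the message, and they count results in the wrong direction. A favourable patient-prompt claim from the all-patient test or the access stratum has a null probability of 3.2% to 4.1%, against 2.5% for the all-patient test alone. The contrast is larger in step 4 because, under the null, the hierarchy rarely reaches the patient step.

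It can also be said that an interaction test would usually miss a real difference. That is true, and it is a reason to rely on the interaction estimate with its interval. It does not make a comparison of stratum p-values informative. Finally, stratified could mean adjusted for access. The next sentence of the plan introduces its adjustments separately, so separate fits are the more natural reading; if adjustment is meant, the sentence still needs rewording.

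**Conclusion.** The point holds as a cheap improvement to a secondary part of the analysis. Separate fits by access cannot show whether a prompt works differently with and without the portal. With equal true effects and 80% overall power, exactly one stratum would be significant in about 43% to 68% of trials, and correlation stronger than 0.2 would take the lower end slightly further down. A prespecified interaction test at 5% would wrongly declare a difference in 5%.

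The rise in false patient-prompt claims from about 0.25% to about 5% is conditional: it arises only if an access-stratum result is treated as a claim, which the plan neither states nor rules out. The results rest on an assumed access share of 50% to 90%, equal arms and equal cluster sizes.

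**What to change.** Replace the sentence on stratified analyses with the following.
- Fit one GEE model on all ITT patients that includes MPM access and its interaction with each prompt.
- Take access from the EMR as recorded before any patient message can be sent. The time point needs care: Study Intervention Phase ties the message to the screening encounter, while Key Eligibility Criteria engages the logic at the visit after cluster assignment. These statements should be reconciled first.
- Report stratum estimates with 95% CIs from that model. Judge any difference by the interaction estimate and its CI, not by comparing stratum p-values.
- Treat access-stratum results as supportive, and the no-access patient-prompt estimate as a negative control that supports no effectiveness claim.
- State that a non-significant interaction is not evidence of equal effects.

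The cost is SAP wording and three model terms (access and two interactions); access is already needed for the planned stratification. The downsides are the low power of the interaction test and that a stratum result can no longer stand alone as a positive finding. Whether to place the access stratum in the hierarchy is a trade-off for the sponsor, because a last position would block it exactly when dilution makes the all-patient test fail. It is not part of this fix.
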